6.5.2 Secondary Analyses

6.5.2.1 Overall Survival

Overall Survival (OS) is defined as the time from randomization to death from any cause. Patients who are not reported as having died at the date of analysis will be censored at the date when they were last known to be alive. Patients who do not have post-baseline information will be censored at the date of randomization.

OS will be analyzed with the same methodologies as PFS. Treatment comparisons will be based on the stratified log-rank test in the ITT population. The null and alternative hypotheses can be phrased in terms of the survival functions $S_{OS_CB-Cabo}(t)$ and $S_{OS_Pbo-Cabo}(t)$ in arm CB-Cabo and arm Pbo-Cabo, respectively:

$$H_0: S_{OS_CB-Cabo}(t) = S_{OS_Pbo-Cabo}(t) \text{ versus } H_1: S_{OS_CB-Cabo}(t) \neq S_{OS_Pbo-Cabo}(t)$$

OS will be tested with a total of two-sided alpha of 0.05 if PFS crosses the efficacy boundary. P-value boundaries of OS are provided in [Table 3](#).

As a sensitivity analysis, the above analyses will be performed using the number of prior TKI cancer therapy (0 vs. ≥ 1) and IMDC prognostic risk group (favorable vs. intermediate vs. poor) and prior PD-1/PD-L1 inhibitor therapy as the stratification factors.

If there is notable imbalance in number of prior lines of anti-cancer therapy between the two treatment arms and if sample size permits, sensitivity analysis will be performed using number of prior lines of anti-cancer therapy (1 vs. 2) and IMDC prognostic risk group (favorable vs. intermediate vs. poor) and prior PD-1/PD-L1 inhibitor therapy as the stratification factors.

Similarly to the primary analysis, to prevent a stratification cell having too few events, if a stratification cell has less than 10 PFS events (two arms combined), the stratification factor of prior PD-1/PD-L1 inhibitor therapy will be removed.

Results from an unstratified analysis will also be provided.

6.5.2.2 Investigator-assessed PFS

Investigator-assessed PFS will be defined and analyzed the same way as the primary efficacy endpoint of IRC-assessed PFS. Disease progression status and date will be determined by investigators instead of IRC.

6.5.3 Additional Analyses

6.5.3.1 Overall Response Rate

Overall response rate (ORR) is defined as the percentage of patients who had an overall response (unconfirmed). An overall response is defined as either complete response (CR) or partial response (PR), as assessed by the IRC according to RECIST v1.1. Patients not meeting these criteria, including patients without any post-baseline evaluable response assessments, will be considered non-responders. Confirmation is not required in this double-blind protocol, but for exploratory purposes ORR with confirmation by IRC will also be summarized. Two CR and PR assessments must be at least 28 days apart without non-response in between, when confirmation is reported.

The analysis population for ORR will be the ITT population. An estimate of ORR and its 95% CI will be calculated with the Clopper-Pearson method for each treatment arm. The difference in ORRs between the two treatment arms and its 95% CI will be computed and compared by Fisher's exact test. The ORR will also be compared between the two arms using the stratified Cochran-Mantel-Haenszel test, stratified by the same factors used in the primary PFS and OS analyses (see [Section 6.5.1](#)).

6.5.3.2 Duration of Response

Duration of Response (DOR) is defined for patients achieving a PR or a CR as the time from the first documented overall response (PR or CR) to the first documented PD as assessed by the IRC according to RECIST v1.1 or death from any cause, whichever

occurs first. Patients who are alive and who have not experienced disease progression at the time of the analysis will be censored at the date of the last evaluable tumor assessment. If no tumor assessments were performed after the date of the first occurrence of the overall response (CR or PR), DOR will be censored at the date of the first occurrence of the overall response. Censoring rules for DOR will follow those in [Table 4](#). The determination of DOR is based on a non-randomized subset of patients (confirmed responders only), and formal hypothesis testing will not be performed. The subset of responders are defined based on post randomization outcomes therefore the responder population is not balanced across the two treatment arms. DOR will be estimated using Kaplan Meier (KM) methodology. Comparisons between treatment arms will be made using the stratified and unstratified log-rank test for descriptive purposes only.

DOR will be reported for patients with confirmed ORR.

6.5.3.3 *Disease Control Rate*

Disease Control Rate (DCR) is defined as the summed percentage of patients with CR, PR or stable disease (SD) documented following randomization according to RECIST v1.1 per IRC.. DCR will be analyzed the same way as ORR.

6.5.3.4 *PFS and OS Rates at Landmark Timepoints*

The PFS rates (according to RECIST 1.1 criteria per IRC) at 6-month, 9-month, and 1-year timepoints are defined as the probabilities the patients are alive and progression free at those timepoints after randomization. The OS rates at 1- and 2- and 3-year landmark timepoints are defined as the probabilities that patients are alive at those time points after randomization. The PFS and OS rate at the landmark timepoints after randomization within the ITT population will be estimated for each treatment arm using Kaplan-Meier methodology, along with 95% CI calculated with the standard error derived from the Greenwood formula.

6.5.3.5 *Patient Reported Outcomes*

Patient-reported outcomes (PRO) for the NCCN-FACT FKSI-19 (Version 2) will be summarized by treatment group. Summary statistics (mean, SD, median, range) of the change from baseline will be provided at each time point. Mean score for each endpoint will be displayed graphically. The analysis will be performed for patients in the PRO-evaluable population, which is defined as ITT with a non-missing baseline assessment and at least one non-missing post-baseline assessment until treatment discontinuation.

With the exception of the visual analog scale (VAS) score and index score for EQ-5D-5L questionnaire, descriptive statistics summarizing the proportions of patients who reported having “no,” “slight,” “moderate,” “severe,” or “extreme/unable” problems at each time point will be reported. The VAS score and the US-specific Index score for EQ-5D-5L questionnaire will be summarized and analyzed as continuous measures. Patients without post-baseline assessments will be excluded from this analysis.

6.5.3.6 *Additional Sensitivity Analyses*

Missing Tumor Assessment

The impact of missing scheduled tumor assessments on PFS may be assessed depending on the number of patients who missed assessments scheduled immediately prior to the date of disease progression per RECIST v1.1. If > 5% of patients missed two or more scheduled assessments consecutively immediately prior to the date of disease progression per RECIST v1.1 in any treatment arm, the following sensitivity analyses will be performed:

Patients who missed two or more scheduled assessments immediately prior to the date of disease progression per RECIST v1.1 or the data cutoff or death will be censored at the last tumor assessment prior to the missed visits.

Statistical methodologies analogous to those used in the primary analysis of PFS as specified in [Section 6.5.1](#) will be used for this sensitivity analysis.

Loss to Follow-up

The impact of loss to follow-up on OS may be assessed depending on the number of patients who are lost to follow-up. If > 5% of patients are lost to follow-up for OS in either treatment arm, a sensitivity analysis will be performed for the comparisons between two treatment arms in which patients who are lost to follow-up will be considered as having died on the date they are lost to follow-up.

6.5.3.7 *Subgroup Analyses*

The consistency of the primary PFS and secondary OS results in subgroups will be examined. The subgroups are defined by the following

- 1) demographics (age [<75 vs ≥ 75], sex [F vs M], and race/ethnicity)
- 2) baseline prognostic characteristics (KPS performance status [70-80, 90-100], IMDC prognostic risk grouping [EDC version], number of organs with metastases [1, 2, ≥ 3], prior nephrectomy, and prior radiotherapy, time from metastatic diagnosis [>1 and ≤ 1 year])
- 3) Prior therapies (previous anti-angiogenic therapies [yes/no], number of prior TKI [1, 2, ≥ 3], prior PD-1/PD-L1 [yes, no], prior nivo/ipi [yes, no], number of prior line of therapy [2, 3])
- 4) Metastatic Sites (lung, lymph node, bone, liver, brain, other as categories)

5) Geographic region (US/ex US)

Summaries of PFS and OS, including unstratified HRs estimated from Cox proportional hazards models and Kaplan-Meier estimates of median PFS and OS, will be produced separately for each level of the categorical variables for the comparisons between treatment arms and displayed in a forest plot (Lewis 2001).

Summaries of ORR by subgroup defined above will also be provided.

Analyses of subgroups with sample size too small may not be performed.

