4.1.1.3 Additional Efficacy Endpoints

The additional efficacy endpoints are:

- Overall response rate (ORR), defined as the percentage of patients with complete response (CR) or partial response (PR) according to the RECIST 1.1 criteria per IRC
- Duration of response (DOR), defined as the time between the first documentation of a PR or a CR to the first documentation of progressive disease (PD) or death, whichever occurs first as determined by RECIST 1.1 criteria per IRC
- Disease control rate (DCR), defined as the summed percentage of patients with CR, PR and stable disease (SD) following treatment initiation according to RECIST 1.1 criteria per IRC.
- PFS rates according to RECIST v1.1 criteria per IRC at 6-month, 9-month and at 1-year landmark timepoints
- OS rate at 1-year, 2-year, and 3-year landmark timepoints
- PFS according to RECIST v1.1 criteria per IRC and OS in subgroups based on demographics and baseline characteristics
- Patient reported outcomes using the NCCN-Functional Assessment of Cancer Therapy (FACT) Kidney Symptom Index (FKSI-19) questionnaire and the EuroQoL 5D utility score (EQ-5D-5L).

- Genetic variants and other biomarkers related to angiogenesis and metabolic pathways

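### SAP 6.5.3.2 reports duration of response only for confirmed responders, so the main (unconfirmed) ORR as a whole has no matching DOR

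*SAP*

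**What the plan says.** SAP 4.1.1.3 (Additional Efficacy Endpoints) lists "Duration of response (DOR), defined as the time between the first documentation of a PR or a CR", ending at PD or death per IRC, and attaches no confirmation condition. SAP 6.5.3.2 opens in the same way: "Duration of Response (DOR) is defined for patients achieving a PR or a CR".

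Later in 6.5.3.2 the analysis set is narrowed. DOR is described as "based on a non-randomized subset of patients (confirmed responders only"), and the section closes with "DOR will be reported for patients with confirmed ORR". The same section also provides for a responder with no tumor assessment after the first response: "DOR will be censored at the date of the first occurrence of the overall response".

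SAP 6.5.3.1 makes the main response rate unconfirmed: "Overall response rate (ORR) is defined as the percentage of patients who had an overall response (unconfirmed"). Confirmation is secondary there: "for exploratory purposes ORR with confirmation by IRC will also be summarized". The confirmation rule is "Two CR and PR assessments must be at least 28 days apart without non-response in between, when confirmation is reported".

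Protocol 14.6.3 does not require confirmation for the ORR comparison, and it presents response duration for responders in each arm without limiting them to confirmed responders. SAP section 3 states that the SAP takes precedence over the protocol.

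**The concern.** The SAP defines DOR for one set of patients and reports it for a smaller one. Readers normally set DOR beside ORR to learn how long the counted responses lasted. Here the main ORR counts every IRC responder, while the DOR covers only those whose response held until a second qualifying assessment.

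Inclusion depends on something that happens after the DOR clock has started. A responder whose disease progresses at the next scan, or who dies before it, is removed from DOR altogether instead of contributing a short duration. Relative to all main-ORR responders, this lifts the early part of the Kaplan-Meier curve in both arms. At stake is the description of response durability, not the trial's inferential result.

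**Working it through.** **Text check**

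| Place in SAP | Patients covered |
|---|---|
| 4.1.1.3, DOR | PR or CR, no confirmation condition |
| 6.5.3.1, main ORR | Unconfirmed CR or PR |
| 6.5.3.1, exploratory ORR | Confirmed CR or PR |
| 6.5.3.2, opening sentence | PR or CR, no confirmation condition |
| 6.5.3.2, no-later-scan censoring rule | Can apply only to an unconfirmed responder |
| 6.5.3.2, analysis set and closing sentence | Confirmed responders |

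A confirmed responder has, by the 6.5.3.1 rule, a second assessment at least 28 days after the first of the pair. The no-later-scan rule can therefore never apply to the set that 6.5.3.2 analyses. It fits only an all-responder DOR. No such DOR is planned anywhere in the SAP.

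**Who is dropped, and does it matter to the curve?**

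- *PD or death before a confirming scan:* in the main ORR, out of DOR. This lifts the curve.
- *Alive, no scan after first response:* would be censored at time zero if included, so the Kaplan-Meier curve is the same either way.
- *Reverts to SD:* out of DOR only if no qualifying pair of response assessments ever occurs. The effect is uncertain.

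**Size (illustration)**

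The documents give no DOR figure to reproduce. Inputs:

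- Scan schedule from SAP section 4: every 8 weeks for 12 cycles (to week 48), then every 12 weeks.
- Days per month: 30.4375, from the PFS formula under SAP Table 4.
- Assumed: median DOR m = 6, 8 or 12 months; Weibull shape k = 1.5 (rising hazard), 1 (constant) or 0.75 (falling); events recorded at the next scan. Only PD or death before confirmation is modelled.

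Formulas: S(t) = 0.5^((t/m)^k). The gap to the next scheduled scan is g = 56/30.4375 = 1.84 months. The share dropped is 1 − S(g). Six months is 26.1 weeks, so the last 8-weekly scan within six months of first response is at 24 weeks (5.52 months). The 6-month rate is S(5.52) for all responders and S(5.52)/S(1.84) for those still in response at the confirming scan.

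Example, k = 1, m = 8: S(1.84) = 0.5^(0.230) = 0.853, so 14.7% are dropped. S(5.52) = 0.5^(0.690) = 0.620, and 0.620/0.853 = 0.727. The rate rises from 62.0% to 72.7%.

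| k | m (months) | Dropped | 6-month rate, all → confirmed |
|---|---|---|---|
| 1.5 | 6 | 11.1% | 54.2% → 61.0% |
| 1.5 | 8 | 7.4% | 67.2% → 72.6% |
| 1.5 | 12 | 4.1% | 80.6% → 84.0% |
| 1 | 6 | 19.1% | 52.9% → 65.4% |
| 1 | 8 | 14.7% | 62.0% → 72.7% |
| 1 | 12 | 10.1% | 72.7% → 80.9% |
| 0.75 | 6 | 24.8% | 52.1% → 69.4% |
| 0.75 | 8 | 20.6% | 59.2% → 74.5% |
| 0.75 | 12 | 15.6% | 67.9% → 80.5% |

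These rates hold for a first response at week 8, 16 or 24, because the scans involved fall by week 48.

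The observed median can fall only on a scan. On the documented 8- then 12-weekly schedule, with first response at week 8, 16 or 24, it shifts by 0 to 2.76 months for k = 1.5, 0 to 2.76 for k = 1, and 2.76 to 5.52 for k = 0.75.

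**The case against.** The strongest reply is that nothing here is contradictory. Section 4.1.1.3 fixes only the start and stop of the interval. Section 6.5.3.2 then names the analysis set twice, so the restriction looks deliberate and the plan can be run as written. Confirmed-responder DOR is a valid companion to the confirmed ORR, which is also reported, so one matched pair exists. The protocol's DOR paragraph neither requires nor waives confirmation, and the SAP supersedes it in any case. DOR carries no formal test.

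Most of this stands, and it sets the severity. It does not remove the mismatch. SAP precedence settles differences from the protocol, not the differences within the SAP. No reason is given for the restriction, the opening definition and the censoring rule were not aligned with it, and the matched pair belongs to the exploratory ORR, not the main one.

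A reader might infer three stronger things that the documents do not support:

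- *That patients in the main ORR get no DOR.* Confirmed responders are a subset of main-ORR responders and do get one. In the illustration they are about 75% to 96% of the total.
- *That the reported median DOR must be longer.* Under a rising or constant hazard it may not move at all.
- *That DOR is biased toward one arm.* The lift applies to each arm, and nothing in the documents shows that it differs between them.

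**Conclusion.** The point holds and is minor. The main ORR as a whole has no matching DOR, and the DOR that is reported is conditional on surviving in response to a later scan while being timed from first response. Its early curve is therefore higher in each arm than that of all main-ORR responders.

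The size rests on assumed medians and hazard shapes. With an 8-week gap, the range is about 4% to 25% of responders dropped and about 3 to 17 percentage points on the 6-month rate. The direction of the early-curve effect does not depend on those assumptions, provided some responders progress or die before confirmation. The PFS analysis, the OS testing that follows it, alpha and power are untouched.

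**What to change.** Before unblinding, amend SAP 6.5.3.2 to report DOR for all IRC responders (the unconfirmed numerator of 6.5.3.1) beside the main ORR, using the no-later-scan censoring rule already written. Report DOR in confirmed responders beside the confirmed ORR, labelled as conditional on confirmation.

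If the sponsor wants only the confirmed version, the minimum is to put the confirmation condition into 4.1.1.3 and the opening sentence of 6.5.3.2, delete the unused censoring rule, and state that the main ORR has no matching DOR. That makes the text consistent but leaves the gap.

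The cost is SAP wording and one extra descriptive table. The downside for the sponsor is that the DOR shown beside the main ORR will probably look shorter.

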10.3 Study Treatment Procedures

For the complete list of schedules of procedures, please refer to the Schedule of Assessments in [Attachment 1](#).

While the patient is receiving study treatment, the patient's clinical status should be evaluated at each clinic visit to confirm that the patient is suitable for continuing study treatment and to make timely decisions regarding the interruption or restarting of study treatment.

Assessments are based on 28-day cycles. *Radiographic evaluation of tumor burden and QoL questionnaires will be performed as scheduled relative to the date of Cycle 1 Day 1 (C1D1) regardless of study treatment holds or delays.* Additional assessments may occur, as clinically indicated, during unscheduled visits.

After randomization, clinic visits for safety evaluations will occur Day 1 of every cycle (approximately every 4 weeks) for the first 12 cycles. Starting with Cycle 13, safety evaluations will occur every 3 cycles (approximately every 12 weeks). More frequent safety evaluations may be performed if clinically indicated. The final scheduled safety assessment will occur at the End of Treatment Visit. If the study treatment is held due to AEs, Investigators should perform additional safety assessments as clinically indicated.

Radiographic evaluation of tumor burden (e.g., diagnostic computed tomography [CT] scan with intravenous contrast or MRI) will occur during Screening (within 28 days prior to randomization), every 8 weeks after C1D1 for the first 12 cycles, every 12 weeks beginning with Cycle 13, and at the End of Treatment Visit. Radiographic assessments may occur more frequently as clinically indicated.

Quality of life questionnaires will be completed before study drug dosing on C1D1, every 4 weeks after C1D1 for the first 12 cycles, every 12 weeks beginning with Cycle 13, and at the End of Treatment Visit.

Patients who hold or discontinue only one of the study drugs (either CB-839/placebo or cabozantinib) for any reason such as, but not limited to, an AE or surgery, should continue the other study drug on study and continue to have scheduled study visits and procedures per protocol.

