14.6.3 Additional Endpoints

Overall Response Rate (ORR)

ORR is defined as the percentage of patients with CR or PR according to the RECIST 1.1 criteria. Response will be adjudicated by the IRC, and response confirmation is not required to compare the two arms in this double-blind protocol. Patients with no evaluable on-study response assessments will be regarded as non-responders. The ORR will be compared between treatment arms by both the Fisher's exact test and a logistic regression analysis accounting for the randomization stratification factors.

Duration of Response (DOR)

For patients achieving a PR or a CR, the duration of response will be calculated as the time between the first documentation of a PR or a CR to the first documentation of PD or death, whichever occurs first. For patients achieving first a PR then a CR, the PR date will be the starting date for response duration calculation. For responders for whom a PD has not been documented yet, [Section 14.6.1](#) conventions regarding PFS censoring will apply. Response duration will be descriptively presented for responders in each treatment arm.

Disease Control Rate (DCR)

DCR is defined as the summed percentage of patients with CR, PR or SD documented at least 8 weeks (-5 day window) following randomization according to RECIST v1.1 criteria.

Patient Reported Outcomes

Patients will be assessed using the NCCN-Functional Assessment of Cancer Therapy (FACT) Kidney Symptom Index ([FKSI-19](#)) questionnaire and the EuroQoL 5D utility score ([EQ-5D-5L](#)) and compared between the two treatment arms. Details of the planned analyses for these outcomes will be provided in the SAP.

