- **Partial Response (PR):** At least a 30% decrease in the sum of diameters of target lesions, taking as reference the baseline sum diameters.
- **Progressive Disease (PD):** At least a 20% increase in the sum of diameters of target lesions, taking as reference the smallest sum on study (this includes the baseline sum if that is the smallest on study). In addition to the relative increase of 20%, the sum must also demonstrate an absolute increase of at least 5 mm. (Note: the appearance of one or more new lesions is also considered progression).
- **Stable Disease (SD):** Neither sufficient shrinkage to qualify for PR nor sufficient increase to qualify for PD, taking as reference the smallest sum diameters while on study.

Special notes on the assessment of target lesions

Lymph nodes: Lymph nodes identified as target lesions should always have the actual short axis measurement recorded (measured in the same anatomical plane as the baseline examination), even if the nodes regress to below 10 mm on study. This means that when lymph nodes are included as target lesions, the ‘sum’ of lesions may not be zero even if complete response criteria are met, since a normal lymph node is defined as having a short axis of < 10 mm. Case report forms or other data collection methods may therefore be designed to have target nodal lesions recorded in a separate section where, in order to qualify for CR, each node must achieve a short axis < 10 mm. For PR, SD, and PD, the actual short axis measurement of the nodes is to be included in the sum of target lesions.

Target lesions that become ‘too small to measure’: While on study, all lesions (nodal and non-nodal) recorded at baseline should have their actual measurements recorded at each subsequent evaluation, even when very small (e.g., 2 mm). However, sometimes lesions or lymph nodes which are recorded as target lesions at baseline become so faint on CT scan that the radiologist

may not feel comfortable assigning an exact measure and may report them as being ‘too small to measure’. When this occurs it is important that a value be recorded on the case report form:

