3 INTRODUCTION

The statistical analysis plan (SAP) provides details of the planned analyses and statistical methods for the study CX-839-008 (A Randomized, Double-Blind, Placebo-Controlled Phase 2 Clinical Trial Comparing CB-839 (Telaglenastat) in Combination with Cabozantinib [CB-Cabo] vs. Placebo with Cabozantinib [Pbo-Cabo] in Patients with Advanced or Metastatic Renal Cell Carcinoma [RCC]). The background and rationale for the study can be found in the study protocol. Statistical analyses including endpoints in the SAP supersedes the protocol.

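### The SAP omits the protocol's 8-week minimum for disease control and gives two start points, so an SD scan before day 51 can count and DCR can come out higher than the protocol's rule would give

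*SAP*

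**What the plan says.** Three places define DCR, and no two agree.

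- Protocol 14.6.3: patients with "CR, PR or SD documented at least 8 weeks (-5 day window) following randomization".
- SAP 4.1.1.3 (endpoint list): "patients with CR, PR and stable disease (SD) following treatment initiation according to RECIST 1.1 criteria per IRC".
- SAP 6.5.3.3 (analysis): CR, PR or "stable disease (SD) documented following randomization according to RECIST v1.1 per IRC", analysed in the same way as ORR. By SAP 6.5.3.1 that means the ITT population, Clopper-Pearson intervals, Fisher's exact test and a stratified Cochran-Mantel-Haenszel test.

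SAP section 3 settles which document governs: "Statistical analyses including endpoints in the SAP supersedes the protocol". The SAP gives no reason for dropping the time condition.

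The RECIST text in Protocol Attachment 5 does not bring the condition back. It defines SD as "Neither sufficient shrinkage to qualify for PR nor sufficient increase to qualify for PD", with the smallest sum on study as reference and no minimum interval.

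**The concern.** SD carries information about disease control mainly through the time over which it is held. Without a minimum, one scan a few weeks after randomization that shows no growth is enough, even if the next scan shows progression. The protocol had guarded against this, and the governing document no longer does.

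Two things are at stake. The reported DCR may differ from the protocol's DCR without the reader being told. And because DCR is compared between arms with formal tests, any difference between arms in how often patients are scanned early would enter that comparison.

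The two start points are a smaller matter of the same kind. A patient randomized but never treated can be counted under SAP 6.5.3.3 and cannot be under SAP 4.1.1.3, although both serve one ITT analysis.

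**Working it through.** The documents state no expected DCR and no power for it, so there is no planned figure to reproduce. The check compares the three definitions with the scan calendar. Days are counted from randomization.

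**Inputs**
- Protocol minimum: 8 weeks less 5 days (Protocol 14.6.3).
- Randomization to C1D1: 0 to 3 days (Protocol 10.2).
- Scans: "every 8 weeks after C1D1 for the first 12 cycles" (Protocol 10.3), window ±5 days (Attachment 1). Extra scans are allowed when clinically indicated.
- End of Treatment visit: 28 to 35 days after discontinuation, with a scan unless one was done in the previous 4 weeks (Attachment 1 and its notes).
- Patients per arm: 208 (Protocol 6.0).

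**Step 1: the protocol cutoff.** 56 − 5 = day 51.

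**Step 2: the first scheduled scan.** Earliest 0 + 56 − 5 = day 51; latest 3 + 56 + 5 = day 64. Every in-window first scan meets the day-51 cutoff. For a patient scanned on schedule, a single scan showing SD counts under the protocol and under the SAP alike.

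**Step 3: where the rules part.** They differ only for patients whose sole evidence of control comes before day 51.
- *Unscheduled or out-of-window scans before day 51.* With SD at week 4 (day 28) and PD at week 8, the SAP counts the patient as controlled and the protocol does not.
- *End of Treatment scans.* To fall on day 50 or earlier, discontinuation must occur by day 50 − 28 = 22 if the visit is at 28 days, or by day 50 − 35 = 15 if it is at 35 days.

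**Step 4: direction.** Every patient who meets the protocol's condition also meets the SAP's, so SAP DCR ≥ protocol DCR in each arm. This holds whether the protocol's 8 weeks is read as applying to SD alone or to CR and PR as well.

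**Step 5: size.** One patient changes an arm's DCR by 1/208 = 0.48 percentage points. The number of such patients is unknown. For illustration only:

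| Affected patients in an arm | Change in that arm's DCR |
|---|---|
| 0 | 0 |
| 1 | 0.48 points |
| 2 | 2/208 = 0.96 points |
| 4 | 4/208 = 1.92 points |

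The effect on the difference between arms is (a − b)/208, where a and b are the affected counts in the two arms. It is zero when a = b.

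**The case against.** The case against making much of this is strong on consequence.

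- The scan calendar is the same in both arms, is fixed to C1D1 whatever the treatment holds, and the trial is double-blind. On that calendar the two rules agree.
- The End of Treatment route needs all treatment to stop within about three weeks. Interruptions of up to 6 weeks are allowed without consulting the Medical Monitor (Protocol 11.1.3.2). A patient who stops one drug continues the other with scheduled procedures (Protocol 10.3).
- Patients who stop for reasons other than progression or death continue to be imaged until progression, death, new therapy or withdrawal of consent (Protocol 10.6.9). Many would still have a week-8 scan, and SD there counts either way.
- DCR is an additional endpoint. The alpha-controlled sequence is IRC-assessed PFS, then OS (SAP 4.2), and no decision rests on DCR.
- IRC methods are in a charter that is not among the documents and may set a minimum interval for SD.

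All of this stands as a limit on size. None of it removes the discrepancy: the SAP text for DCR does not point to a charter rule, and a patient with SD at week 4 and PD at week 8 still counts.

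A reader might go further and infer that DCR will be inflated, that by some particular percentage, or that the comparison between arms is biased because a drug is added in one of them. The documents support none of these. They give no rate of early scans or of early full discontinuation, and no sign that either differs by arm.

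**Conclusion.** The discrepancy is real and sits in the governing document. As written, the SAP's DCR can equal or exceed the protocol's but cannot fall below it, by 0.48 points for each affected patient in an arm of 208. The number affected may be zero and is probably small, since it is confined to off-schedule scans before day 51 and to End of Treatment scans after full discontinuation by about day 22, with no later qualifying scan. Bias between arms is conditional on a difference in early scanning or early full discontinuation. This is a low-severity point about an endpoint outside the type I error control, worth correcting because three definitions of one endpoint should not go to programming. The conclusion assumes that no unseen document sets a minimum interval for SD.

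**What to change.** In SAP 4.1.1.3 and 6.5.3.3, use one definition:

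- Start point: randomization in both sections.
- Controlled: IRC-assessed CR or PR at any time, or SD on a scan no earlier than 8 weeks less 5 days (day 51) after randomization.
- Not controlled: patients whose only evidence is an SD scan before that day.

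The wording should attach the time condition to SD expressly. The protocol's sentence can be read as applying it to CR and PR too. On that reading, a patient with an unconfirmed PR on an early scan and PD at week 8 would be a responder for ORR yet not disease-controlled.

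If the sponsor dropped the minimum on purpose, the SAP should say so, give the reason, and report DCR under both definitions.

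The cost is two sentences in the SAP. No patient scanned on schedule is lost; the only downside is a DCR that may be slightly lower.
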